# **Number of subjects**

This trial will include 1,200 subjects.

# **Subject inclusion conditions**

Subjects must meet the following three conditions:

- A. aged 21 years and above (inclusive) and below 65 years old (inclusive) who have not undergone total hysterectomy and uterine / cervical radiation therapy
- B. Understand the trial content and sign the subject consent form
- C. Those who meet one of the following 5 conditions:
- 1. Those with no abnormal smears or history of cervical lesions
- 2. Those who have had mild smear or pathological tissue abnormalities within 3-12 months and need to undergo cervical smear follow-up

Mild smear abnormalities include atypical squamous cells of undetermined significance, cervical intraepithelial neoplasia grade 1, or atypical glandular cells.

3. Have had moderate to severe smear or pathological tissue abnormalities or cervical cancer, have undergone cone surgery, and are currently being followed

Including smear is atypical squamous cells favor high-grade squamous intraepithelial lesion atypical squamous cells favor high-grade squamous intraepithelial lesion, the cytopathology cannot exclude high-grade squamous intraepithelial lesion dysplasia cannot exclude high-grade squamous intraepithelial lesion, smear or histopathology is Cervical intraepithelial neoplasia grade 2, Cervical intraepithelial neoplasia grade 3, Cervical carcinoma in situ, Cervical squamous cell carcinoma, or atypical glandular cells favor neoplasm, cervical adenocarcinoma in situ, or cervical adenocarcinoma.

4. Those who have mild smear or pathological tissue abnormalities within 3 months and have not yet been treated

Mild smear abnormalities include atypical squamous cells of undetermined significance, cervical intraepithelial neoplasia grade 1, or atypical glandular cells.

5. Those who have found moderate to severe smear or pathological tissue abnormalities or cervical cancer within 3 months and have not yet received treatment

Including smear shows atypical squamous cells favor high- grade squamous intraepithelial lesion, smear test or histopathology is Cervical intraepithelial neoplasia grade 2, Cervical intraepithelial neoplasia grade 3, Cervical carcinoma in situ, Cervical squamous cell carcinoma, or atypical glandular cells favor neoplasm, cervical adenocarcinoma in situ, or cervical adenocarcinoma.

The above groupings are also the basis for stratification of the statistical analysis of this trial.

# **Subject exclusion conditions**

## Subjects with any of the following conditions will not be able to participate in this trial:

- A. Those who have undergone total hysterectomy (those who have undergone subtotal hysterectomy and still have a cervix do not need to be excluded)
- B. Pregnant
- C. Women with cervicitis who must receive treatment
- D. Those who have received treatment for cervical lesions within 90 days
- E. who have received or are currently receiving uterine / cervical or vaginal radiation therapy
- F. less than 21 years old or over 65 years old
- G. Having sex without condom within 8 hours
- H. Excessive vaginal secretions, such as excessive clear mucus during ovulation
- I. Those who are receiving local treatment for vaginitis and have medicine in their vagina
- J. During the menstrual period, the menstruation has not ended yet

#### **Evaluation indicators**

#### **Main evaluation indicators:**

- A. HPV16, 18, 31, 33, 35, 39, 45, 51, 52, 56, 58, 59, 66, 68 are cancer-causing high-risk types. The agreement on detecting the presence of high-risk HPV between physician-sampled specimens and self-collected specimens is listed as the main purpose. Consistency is defined as follows:
- B. The high-risk HPV test results are consistent (agree). The test results indicate that either of the above-mentioned high-risk HPV types is present in both cases or that neither of them has high-risk HPV types.
- C. The high-risk HPV test results are inconsistent (disagreement). One of the samples collected by the doctor or self-sampling
- D.

- E. does not have any of the above-mentioned high-risk HPV types, and the other has any of the above-mentioned high-risk types.
- F. The consistency between the test results of the specimens collected by the physician and those collected by the subject will be evaluated by Cohen 's kappa coefficient or compared by related tests.

#### **Secondary evaluation indicators:**

- A. The success rate of HPV typing (proportion of effective specimens) for physician-collected and self-collected specimens.
- B. of all detectable HPV types.
- C. The incidence of adverse reactions is used as a safety evaluation index to evaluate whether adverse reactions will occur when a doctor's examination or a woman's self-sampling of vaginal secretions will occur. The test process is recorded according to the CTCAE version 5.0 grading standards
- D. Evaluate whether women can complete effective self-sampling by following the instructions or videos. The beta-globin of the test results will be used as the evaluation index of the effective specimen, and the results of the questionnaire survey will be used to evaluate the reliability of the description file.
- E. The self-collection success rate (proportion of effective specimens) and consistency assessment of each group under the test group.
- F. Correlation between the HPV test results collected by doctors, the HPV test results of self-collected specimens, and the cervical smear and histopathological diagnosis results at the same time. Taking the most severe pathological diagnosis as the standard, calculate separately
- 1. Sensitivity, specificity, positive predictive value and negative predictive value for predicting cervical lesions based on HPV test results collected by physicians
- 2. Sensitivity, specificity, positive predictive value and negative predictive value for predicting cervical lesions based on test results of self-collected specimens
- G. Through questionnaires, subjects' self-sampling satisfaction was assessed.

#### Statistical methods

This study is a multi-center, operator-blinded clinical trial in Taiwan . It mainly explores the consistency of self-sampling of the product and that of doctors . This trial will use the test results of samples collected by doctors as the standard and compare them with the HPV type test results

of self-collected specimens from the same subject to verify the HPV types in the samples collected by doctors and self-sampling. consistency.

A. The trial design uses the status of cervical precancerous lesions as a stratification variable. Five groups of subjects will be recruited according to the following proportions. It is expected to recruit a total of 1,200 subjects:

The 5 groups of subjects included in the study	Inclusion ratio	Estimated number of people to be included
1. Those with no abnormal smears or history of cervical lesions	10%	120 people
2. Those who have had mild smear or pathological tissue abnormalities within 3-12 months and need to undergo cervical smear follow-up	15%	180 people
3. Have had moderate to severe smear or pathological tissue abnormalities or cervical cancer, have undergone cone surgery, and are currently being followed	20 %	240 people
4. Those who have mild smear or pathological tissue abnormalities within 3 months and have not yet been treated	20 %	240 people
5. Those who have found moderate to severe smear or pathological tissue abnormalities or cervical cancer within 3 months and have not yet received treatment	35%	420 people
The total number of subjects expected to be included		1,200 people

Based on clinical research, it is estimated that the HPV positivity rates in the above five groups are (1) 10%, (2) 70%, (3) 50%, (4) 70%, and (5) 90% respectively. Based on the experimental design, under the stratified recruitment ratio, the overall HPV positivity rate is expected to be approximately 67%.

- B. According to the main evaluation indicators of the test, the consistency of this study is defined as:
- 1. HPV16, 18, 31, 33, 35, 39, 45, 51, 52, 56, 58, 59, 66, 68 are cancer-causing high-risk types. The agreement on detecting the presence of high-risk HPV between physician-sampled specimens and self-collected specimens is listed as the main purpose. Consistency is defined as follows:
- (1) The high-risk HPV test results are consistent (agree). The test results indicate that either of the above-mentioned high-risk HPV types is present in both cases or that neither of them has high-risk HPV types.
- (2) The high-risk HPV test results are inconsistent (disagreement). One of the samples collected by the doctor or self-collected does not have any of the above-mentioned high-risk HPV types, and the other has any of the above-mentioned high-risk types.
- 2. The consistency between the test results of the specimens collected by the physician and the specimens collected by the subjects will be evaluated by Cohen 's kappa coefficient or related test comparisons.
- C. The consistency assessment will use valid samples as the analysis group, that is, the samples collected by the verification physician and the self-collected specimens of the same subject are both valid samples. Valid specimens are defined as those who test positive for the  $\beta$ -globin gene in the internal control group of the [name] Papillomavirus Genotyping Test Kit.
- D. Safety, self-sampling success rate, and satisfaction evaluation are based on the intent-to-treat population (ITT).

## **Study purpose**

"HygeiaTouch Self Sampling Kit for Women " was developed and commissioned by Hygeia Touch Inc. This kit contains a self-sampling swab, designed for oriental women, made of non-toxic and non-allergenic materials, and can be used for self-collection sufficient vaginal exfoliated cells for HPV testing. This product is a single use product, which is easy to operate and allows women to take specimens freely and comfortably. The collected samples can be sent to a professional laboratory at room temperature for high-risk HPV typing test . Providing women with cervical screening an alternative will increase cervical screening rates nationwide and further reduce the incidence of cervical cancer.

In order to verify the consistency of the high-risk HPV test results between the samples collected by women using this kit and the samples collected by doctors from the cervix , 1,200 women will be included in this experiment, and they will undergo self- collection and doctor -collected inspections respectively. The test results of the samples collected by doctors will be used as the standard to evaluate the consistency of HPV typing results between the samples obtained by using the self- collection kit group and the samples collected by doctors . This product has been classified by the Food and Drug Administration of the Ministry of Health and Welfare, and it has been judged as a class 2 medical device. If the test results show a high degree of consistency between the self- collection and the doctor's test , it will be used to apply to the Ministry of Health and Welfare that this set can be used as a second-level medical device inspection registration for women's self- collection for high-risk HPV typing .

### **A. The main purpose of the test primary objective:**

For the test group, the consistency (agreement) of whether there is high-risk HPV detected by using the samples obtained by the self-collection kit and the samples collected by the doctor . Consistency definitions are described in Section 6.3.

### **B. Secondary objectives of the test :**

1. Evaluate whether women can complete effective self-specimen sampling by following the instructions or videos.
2. Safety assessment of sampling, including physician and self - examination
3. collection success rate, consistency evaluation and comparison of each group
4. the correlation between the HPV test results of physician's test /self- test and the results of smear and histopathological diagnosis
5. Self -test satisfaction assessment

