#### B. Secondary objectives:

- 1. Determine if women can effectively perform self-sampling by following provided instructions or videos.
- 2. Assess the safety of testing, including evaluations by physicians and self-sampling.
- 3. Evaluate the success rate of self-sampling, consistency, and compare results among different groups.
- 4. Examine the correlation between HPV test results selected by physicians or self-sampling, and compare with smear and histopathological diagnosis results.
- 5. Evaluate satisfaction with self-sampling.

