## **Outcome measures**

### **Primary evaluation indicators:**

- A. HPV16, 18, 31, 33, 35, 39, 45, 51, 52, 56, 58, 59, 66, 68 and other 14 types are high-risk cancer-causing types. Therefore, the main purpose of the agreement is whether there is high-risk HPV detected in the samples collected by doctors and self - sampled . Consistency is defined as follows:
- B. The high-risk HPV test results are consistent (agree) , and the test results show that both of them have any of the above-mentioned high-risk HPV or neither of them has high-risk HPV .
- C. The test results of high-risk HPV are inconsistent ( disagree ). One of the samples collected by doctors and self- collected samples does not have any of the above-mentioned high-risk HPV types , and the other has any of the above-mentioned high-risk types.
- D. The consistency between the test results of the samples collected by the physician and the test results of the subjects' self- collected samples will be evaluated by Cohen 's kappa coefficient or compared with related tests.

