## Statistical considerations

### Statistical design, methods and analysis procedures

A. This study is a multi-center clinical trial in Taiwan to test the blindness of operators . It mainly explores the consistency between self- testing of products and doctor -testing . In this experiment, the test results of samples collected by doctors will be used as the standard, and compared with the results of HPV type test of samples collected by the same subject to verify the consistency of HPV types in samples collected by doctors and self- sampled samples.

B. The experimental design uses the status of cervical precancerous lesions as a stratification variable, and the 5 groups of test groups are divided into the following proportions:

5 groups of subjects included in the subjects	Inclusion ratio
1. No history of abnormal smear or cervical lesions	10%
2. There have been mild smears or pathological abnormalities within 3-12 months, and those who need to receive Pap smear follow-up	15%
3. Those who have had moderate to severe smear or pathological abnormalities or cervical cancer, have received conical surgery , and are currently receiving follow-up	20 %
4. Mild smears or pathological tissue abnormalities within 3 months, who have not yet been treated	20 %
5. Moderate and severe abnormalities in smear or pathological tissue or cervical cancer found within 3 months, and those who have not received treatment	35%

According to relevant literature research, it is estimated that the positive probability of HPV in the five groups is (1) 10% , (2) 70% , (3) 50%, ( 4 ) 70% , ( 5 ) 90%, depending on the experimental design Under the stratum recruitment ratio , the overall HPV positive rate is expected to be about 67% , as shown in the table below .

Stratification	AI location rate	S stratified HPV positive prob.
1. No history of abnormal smear or cervical lesions	0.1	0.1
2. There have been mild smears or pathological abnormalities within 3-12 months, and those who need to receive Pap smear follow-up	0.15	0.7

3. Those who have had moderate to severe smear or pathological abnormalities or cervical cancer, have received conical surgery , and are currently receiving follow-up	0.20	0.5
4. Mild smears or pathological tissue abnormalities within 3 months, who have not yet been treated	0.20	0.7
5. Moderate and severe abnormalities in smear or pathological tissue or cervical cancer found within 3 months, and those who have not received treatment	0.35	0.9

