## Sample size calculation

The above-mentioned kappa value is preset to be 0.72, under the condition that the test power is 80% and the significance level is 0.05, according to the proportion of subjects included in each group, the required samples are 1,049 cases . Considering that there are up to 10% of invalid samples and patients requesting to withdraw from the trial, the trial is expected to recruit 1,200 subjects , and the number of subjects assigned to each group is as follows according to the original test group ratio.

5 groups of subjects included in the subjects	Inclusion ratio	Estimated number of people included
1. No history of abnormal smear or cervical lesions	10%	120 people
2. There have been mild smears or pathological abnormalities within 3-12 months, and those who need to receive Pap smear follow-up	15%	180 people
3. Those who have had moderate to severe smear or pathological abnormalities or cervical cancer, have received conical surgery, and are currently receiving follow-up	20 %	240 people
4. Mild smears or pathological tissue abnormalities within 3 months, who have not yet been treated	20 %	240 people
5. Moderate and severe abnormalities in smear or pathological tissue or cervical cancer found within 3 months, and those who have not received treatment	35%	420 people
The total number of subjects expected to be included		1,200 people

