Reactive changes: Inflammation, repair, radiation, and others												
Atrophy with inflammation												
Atypical squamous cells (ASCUS)												
Atypical glandular cells												
Mild dysplasia (CIN1) with koilocytes												
Mild dysplasia (CIN1) without koilocytes												
Moderate dysplasia (CIN2)												
Severe dysplasia (CIN3)												
Carcinoma in situ (CIN3)												
Squamous cell carcinoma												
Adenocarcinoma												
Other malignant neoplasm												
Other												
Atypical glandular cells favor neoplasm												
Atypical squamous cells cannot exclude HSIL												
Dysplasia cannot exclude HSIL												
Endocervical adenocarcinoma in situ												

Table 4 Consistency of high-risk HPV detection in all cases

Physician-collected		Kappa statistic (95% CI)	p value	Overall Agreement
Self-collected	Positive	Negative		
Positive				
Negative				

High-risk HPV types include 16, 18, 31, 33, 35, 39, 45, 51, 52, 56, 58, 59, 66, 68 and other 14 types. The definition of consistency is as follows: high-risk HPV test results are concordant (concordant), the test results of the subject's physician -collected sample and self- collected sample both have any of the above-mentioned high-risk HPV (high-risk HPV positive) or both have no high-risk HPV (high-risk HPV negative); high-risk HPV test results are inconsistent (discordant), the test results of the subject's doctor-collected sample and self-collected sample, one does not have any high-risk HPV, and the other has any of the above- mentioned high -risk types .

Table 5 Consistency of high-risk HPV types detected in each group

Self-collected	Physician-collected		Kappa statistic (95% CI)	p value	Overall Agreement
	Positive	Negative			
Group 1					
Positive					
Negative					
Group 2					
Positive					
Negative					
Group 3					
Positive					
Negative					
Group 4					
Positive					
Negative					
Group 5					
Positive					
Negative					

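### Kappas set side by side across the five groups in Table 5 are likely to suggest differences in consistency that come from HPV positivity, not from self-sampling

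*SAP*

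**What the plan says.** Both documents make the group comparison a secondary objective. The SAP's item 3 reads "consistency evaluation and comparison of each group"; the protocol's item 3 reads "Evaluate the success rate of self-sampling, consistency, and compare results among different groups". Consistency by group returns in the SAP as secondary indicator D and as item E of the secondary indicators to be analyzed. The SAP reserves the exploratory label for analyses outside the primary and secondary indicators, so this one is not exploratory.

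The SAP's primary evaluation indicators say that consistency "will be evaluated by Cohen 's kappa coefficient or compared with related tests"; the related tests are not named. The output by group is "Table 5 Consistency of high-risk HPV types detected in each group". For each group it has the 2x2 counts, kappa with a 95% CI, a p value and overall agreement. Kappa is the only statistic there whose heading carries an interval. The null hypothesis behind each p value is not stated.

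The protocol estimates that "the HPV positivity rates in the above five groups are (1) 10%, (2) 70%, (3) 50%, (4) 70%, and (5) 90% respectively", and the SAP repeats these rates. Neither document says how kappa is to be read across groups with such different rates.

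**The concern.** Kappa corrects observed agreement for chance agreement, and the SAP builds chance agreement from the table margins. When nearly everyone is positive or nearly everyone is negative, chance agreement is high, and the same error rates usually give a lower kappa. Here the expected rates run from 10% to 90%, so group kappas are not on a common footing.

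A reader of Table 5 could conclude that self-sampling agrees poorly with the physician specimen in Group 1 (women with no history, arguably closest to the screening use in the study purpose) and in Group 5 (untreated moderate to severe lesions), although performance is the same there. A real difference could equally be masked. The only kappa benchmark in the SAP is 0.66, which invites reading each group against it.

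**Working it through.** **The plan's own figures.** Positivity: 0.10×0.1 + 0.15×0.7 + 0.20×0.5 + 0.20×0.7 + 0.35×0.9 = 0.67, which matches "overall HPV positive rate is expected to be about 67" percent. For sample size the SAP says "kappa value is preset to be 0.72, under the condition that the test power is 80% and the significance level is 0.05", with null 0.66. Using N = [1.645·√V(0.66) + 0.842·√V(0.72)]² / 0.06², equal margins of 0.67, one-sided 0.05 and the full large-sample kappa variance, N = 1,049, as stated. The simpler variance printed in the SAP gives 1,064. The pooled design is therefore reproduced.

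**Inputs for the group check.** The positivity rates π are the plan's. The documents give no error rates, so these are assumptions, held identical in all five groups: Se is the share of physician-positive women who are self-positive, and Sp the share of physician-negative women who are self-negative.

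**Formulas.** In the SAP's table layout, a = π·Se, b = (1−π)(1−Sp), c = π(1−Se), d = (1−π)·Sp. Then P0 = a + d, Pc comes from the margins, and K = (P0 − Pc)/(1 − Pc).

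**Worked example, Se 0.9076 and Sp 0.8124 (pooled kappa 0.72).**
- Group 1, π = 0.1: P0 = 0.0908 + 0.7312 = 0.8219. The self-positive margin is 0.2596, so Pc = 0.2596×0.1 + 0.7404×0.9 = 0.6923, and K = 0.1296/0.3077 = 0.42.
- Group 3, π = 0.5: P0 = 0.86, Pc = 0.50, K = 0.36/0.50 = 0.72.

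**Kappa by group under identical performance.**

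| Se / Sp (assumed) | Pooled | G1 | G2 | G3 | G4 | G5 | Spread |
|---|---|---|---|---|---|---|---|
| 90.8% / 81.2% | 0.72 | 0.42 | 0.71 | 0.72 | 0.71 | 0.56 | 0.30 |
| 87.2% / 87.2% | 0.72 | 0.51 | 0.71 | 0.74 | 0.71 | 0.51 | 0.23 |
| 95% / 74.1% | 0.72 | 0.34 | 0.72 | 0.69 | 0.72 | 0.64 | 0.38 |
| 82% / 95.9% | 0.72 | 0.72 | 0.70 | 0.78 | 0.70 | 0.46 | 0.32 |
| 95% / 95% | 0.89 | 0.76 | 0.88 | 0.90 | 0.88 | 0.76 | 0.14 |

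At pooled kappa 0.72 the spread is 0.23 to 0.38, about four to six times the 0.06 between the null and the expected value.

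**Overall agreement.** In the first row it is 82%, 88%, 86%, 88% and 90%. When Se = Sp it is the same in every group (87.2% in the second row).

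**Reading against 0.66.** Planned group sizes less 10% give 108, 162, 216, 216 and 378 pairs. In simulation under the first two rows, the observed kappa fell below 0.66 in over 90% of trials in both Group 1 and Group 5, against roughly 5% to 21% in Groups 2 to 4.

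**Whether conditioning on the physician result cures this.** Suppose both specimens measure true HPV status with independent errors, each with sensitivity and specificity 0.931 in every group, and take the plan's rates as true prevalence. Pooled kappa is again 0.72. In Group 1, the share self-positive among physician-positives is (0.1×0.931² + 0.9×0.069²)/(0.1×0.931 + 0.9×0.069) = 0.0910/0.1552 = 0.59. In Group 5 the same formula gives 0.92. Negative agreement runs the other way, 0.92 in Group 1 and 0.59 in Group 5. Overall agreement is 0.872 in all five groups. Positive and negative agreement therefore also move with positivity once the physician specimen has error.

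**The case against.** The strongest reply is that the plan does not do what a reader might infer. Three stronger readings are tempting.

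- **That the trial would formally declare the groups different.** In simulation, a 5% test of equal kappas rejects in 82% and 85% of trials under the first two sets of rates, and in 52% at 95%/95%, although performance is identical. The SAP contains no such test. Every entry in Table 5 is computed within one group, comparison appears only in the objective line, and 0.66 is applied only to the pooled kappa. The risk is misreading, not a planned false-positive procedure. This part of the reply stands.
- **That the comparison rests on kappa alone.** Table 5 also gives overall agreement and the 2x2 counts. When both error rates are equal, overall agreement is constant across groups and exposes the artefact. This stands in part: with unequal rates overall agreement drifts too, and nothing tells the reader to prefer it.
- **That a joint test conditional on the physician result would be a sound replacement.** It holds its level only if the physician result is treated as error-free. Under the two-specimen error model above it falsely rejected in 99.9% of simulated trials, against 84% for the kappa test. The documents call the physician result the standard but give no error rate for it, so they do not support that replacement.

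It is also fair that the size depends on assumed rates, that Group 1 is unaffected at 82%/95.9%, and that trial success depends only on the pooled kappa.

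**Conclusion.** The concern holds as one of interpretation. A stated secondary objective compares consistency between groups, the only named measure depends on positivity, and the plan's own rates make that dependence large. With identical performance and pooled kappa 0.72, the first two sets of assumed rates put Group 1 at about 0.42 to 0.51, Groups 2 to 4 at 0.71 to 0.74, and Group 5 at 0.51 to 0.56. The pattern shifts with the rates and shrinks at high performance. Side-by-side kappas are likely, not certain, to suggest differences that are not there. Groups 2 and 4, both expected at 70%, remain comparable. The pooled primary test and its sample size are unaffected.

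**What to change.** In SAP secondary objective 3, secondary evaluation indicator D, item E of the secondary indicators to be analyzed, and the Table 5 notes:

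1. State that group kappas are descriptive, are not compared between groups, and are not read against 0.66.
2. Add to Table 5, from the counts already there, positive, negative and overall percent agreement with the physician result, each with a 95% CI. Note that these are descriptive too, because they can also shift with positivity.
3. State the null hypothesis that each Table 5 p value tests.

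Do not add a joint test conditional on the physician result.

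The cost is SAP wording and a few columns; no new data and no change in sample size. Intervals will be wide in two cells: about 11 physician-positives in Group 1 (108×0.1) and about 38 physician-negatives in Group 5 (378×0.1). The trial also gives up any formal between-group claim.
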